17.6 Analysis of Outcomes

Analyses of mechanistic outcomes will be largely exploratory and completed by the laboratory team. In each Tier, summary measures of readouts from samples will be provided: means and SDs, or medians and IQRs as appropriate. Summaries will be reported separately for each time point and each treatment group, as well as pooled across treatment groups.

Subsets of sample readouts to include in the statistical models will be determined through clinical opinion and principal component analysis (PCA). Across the tiers, the longitudinal trajectories of the sample readouts will be analysed through linear mixed effects models. Associations between longitudinal samples and exacerbation rates will be explored through negative binomial mixed effects models. Model based estimates of time and treatment effects will be reported along with 95% confidence intervals and p-values from two-sided tests. Visual plots of fitted values will be provided to aid interpretation.

In Tier 2, additional analysis, through linear mixed effects models, will explore the associations between the DBS elute antibodies collected in Tier 2 and those in Tier 1. These analyses will include any new metabolites identified in Tier 2.

Associations between immune responses to BCG vaccination and exacerbations will be explored through negative binomial mixed effects models. Model based estimates of time and treatment

effects will be reported along with 95% confidence intervals and visual plots of fitted values to aid interpretation.

Exploratory identification of risk factors for exacerbation (classed as a binary yes/no outcome) will be performed using logistic regression modelling. Candidate predictors identified from clinical expertise and through analysis of samples in Tier 3 (and potentially Tiers 1 and 2) will be included in the model. Model performance will be reported through the C-index and Brier score. Calibration slopes will be plotted. Model overfitting will also be estimated, and optimism-adjusted estimates will be produced.

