- quality of life (QOL), as defined by the COPD Assessment Test (CAT)
- total number of days of antibiotic therapy for AECOPD during follow up
- total number of days of oral steroid therapy for AECOPD during follow up
- type of exacerbation (as they occur (rate over time)):
 - □ defined by Anthonisen criteria
 - defined by a clinical adjudication committee (CAC), who will use sputum, viral and symptom data to determine aetiology of each event

Mechanistic Analyses

BCG vaccine-specific responses comprised of trained immunity, gene expression analyses, cell phenotyping and functional screening.

- Based on analysis of dried blood spot (DBS) samples at baseline, 1, 3, and 12 months:
 - □ anti-BCG antibody responses
 - \Box cytokine profiles (IL-1 β , IL-6, TNF α , IL-10)
- Based on whole blood, dried blood spot (DBS), peripheral blood mononuclear cells (PBMC), neutrophils, serum, and PAXgene tubes at baseline, 1, 3, and 12 months:
 - □ antigen-specific B cell & antibody
 - $\hfill\square$ trained immunity
 - □ serum cytokine analysis
 - □ transcriptomics
 - □ flow cytometry
- Based on sputum, saliva, nasal swab, and DBS samples following exacerbation:
 - □ microbiology profile (multiplex PCR, bacterial culture)
 - anti-pathogen antibody responses (Immunoglobulin G (IgG)/ Immunoglobulin A (IgA))
 - □ anti-BCG antibody responses
 - Cytokine profiles (IL-1, IL-6, TNFα, IL-10)

TRIAL SCHEMA

STABILISE: a multicentre, randomised, parallel group, superiority trial to inveSTigAte the use of BCG vaccine In aLtering Immune reSponse and Exacerbation in chronic obstructive pulmonary disease (COPD)

*Mechanistic subgroup only

[±] Both groups to provide exacerbation samples unless patient opts out

LIST OF CONTENTS

1. BAG	CKGROUND AND RATIONALE

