2.2 Main trial objectives

2.2.1 Clinical aims and objectives

The primary objective of the trial is to determine whether BCG vaccination reduces rates of moderate-severe AECOPD over 12 months in patients who have a clinical diagnosis of COPD, and a history of exacerbation in the preceding year. Our hypothesis is that the vaccine will reduce infectious exacerbations, and that there may be a greater effect for viral driven events.

The secondary clinical objectives are to compare the rate of hospitalisations for infective exacerbations, QOL, total number of days of antibiotic and steroid therapy use during the follow up period between intervention and control groups and to determine the acceptability of the BCG vaccine.

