17.4.3 Tier 3 outcomes (all exacerbations)

All outcomes will be recorded whenever a participant experiences an exacerbation and provides sputum, saliva, nose/throat swabs, and DBS samples.

Anti-BCG antibody responses, as obtained from ELISAs to detect IgG, IgA and IgM responses to whole BCG organism, proteinaceous (Ag85) and a non-proteinaceous (Lipoarabinomannan) antigen

- Cytokines: IL-1B, IL-6, TNFα and IL-10
- Type of pathogen present (bacteria, virus) and specific species
- IgG and IgA response to any identified pathogen

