17.5 Sample Size

Tier 1 will consist of the whole cohort of 804 participants as for the main RCT.

Tier 2 will consist of the first 80 participants who have consented to provide samples for the detailed sub-study. Since consent to participate in the detailed mechanistic sub-study is a minimisation criterion, these 80 participants will be well balanced in terms of allocated treatment arm and the other minimisation criteria (see Section 6 – enrolment, randomisation and blinding).

Tier 3 will consist of all participants who experience an exacerbation and provide sputum, saliva, nose/throat swabs and DBS samples. We anticipate we will collect data on around 1300 exacerbations from the 804 participants.

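### Section 17.6, read plainly, plans treatment-effect tests on Tier 3 readouts, where a BCG effect on the immune response cannot be separated from a change in which exacerbations are sampled

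*Protocol*

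**What the plan says.** Section 17.6 sets one modelling approach for the mechanistic readouts: "Across the tiers, the longitudinal trajectories of the sample readouts will be analysed through linear mixed effects models". On reporting it says: "Model based estimates of time and treatment effects will be reported along with 95% confidence intervals and p-values from two-sided tests". Neither sentence excepts a tier. The section calls the mechanistic analyses largely exploratory and gives them to the laboratory team.

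The tiers are sampled differently. Tiers 1 and 2 are sampled at scheduled times from baseline to 12 months (17.4.1, 17.4.2). For Tier 3, section 17.4.3 says: "All outcomes will be recorded whenever a participant experiences an exacerbation and provides sputum, saliva, nose/throat swabs, and DBS samples". Section 17.5 repeats this as the definition of the tier: "Tier 3 will consist of all participants who experience an exacerbation and provide sputum, saliva, nose/throat swabs and DBS samples". One Tier 3 outcome carries a further condition, that a pathogen was found: "IgG and IgA response to any identified pathogen".

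Section 2.2.1 says what BCG is expected to do to these events: "Our hypothesis is that the vaccine will reduce infectious exacerbations, and that there may be a greater effect for viral driven events".

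**The concern.** Randomisation protects a comparison of all participants at a scheduled time. It does not protect a comparison among events that happen after randomisation and that the intervention is meant to prevent. Entry to Tier 3 depends on having an exacerbation, the event counted by the primary outcome, and then on returning samples.

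If BCG prevents viral events more than others, the exacerbations left in the BCG arm are a different mix from those in the control arm. Any readout that differs between event types, or between people who do and do not exacerbate, will then differ by arm even if BCG does nothing to the readout itself. This is plausible for cytokines and close to built in for antibody to whichever pathogen was found.

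Sample return adds a second selection step. Participants are told their allocation (6.5), and the trial schema says: "Both groups to provide exacerbation samples unless patient opts out". Section 7.3 also makes exacerbation sampling subject to consent, whereas section 17.3 says all enrolled patients will have consented to it.

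At stake is a significant Tier 3 treatment effect being taken as evidence of how BCG acts when it may only reflect which events were prevented.

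**Working it through.** **1. The plan's own figures.** Inputs from section 14.1: rates 2.25 and 1.8 per person-year, dispersion k = 0.36, two-sided 5%, 90% power, one year of exposure. With V0 = 2/2.025 + 2(0.36) = 1.708 (null variance at the average rate) and V1 = 1/2.25 + 1/1.8 + 2(0.36) = 1.720:

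n = (1.960·√1.708 + 1.282·√1.720)² / (ln 0.8)² = 361.4 per group.

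The plan has 361, and 361/0.9 = 401.1 gives its 402. The rates and dispersion can therefore be used as stated.

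**2. The Tier 3 count.** Section 17.5 says: "We anticipate we will collect data on around 1300 exacerbations from the 804 participants". Expected events are 402 × (2.25 + 1.8) = 1,628, and 1300/1,628 = 0.80. The plan's count thus corresponds to about 80% of events being sampled. With 361 per group it is 1300/1,462 = 0.89.

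**3. Who can enter Tier 3.** Under the plan's negative binomial model, P(at least one event in a year) = 1 − (1 + k·r)^(−1/k). Control: 1 − 1.81^(−2.78) = 0.81. BCG: 1 − 1.648^(−2.78) = 0.75. If the trial's target effect is real, the arms differ in who can contribute.

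**4. Shift in event mix.** The protocol gives no viral share, no type-specific effects and no readout differences, so these are assumptions. Take a 50% viral share in controls, a viral rate ratio of 0.60 and a non-viral rate ratio of 1.00. The overall ratio is 0.5(0.60) + 0.5(1.00) = 0.80, the plan's target. The viral share on BCG is 0.30/0.80 = 37.5%, against 50% on control. If viral and non-viral events differ by d SD in the readout, the spurious arm difference is (0.375 − 0.50)·d = −0.125d: −0.0625 SD at d = 0.5 and −0.125 SD at d = 1.

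**5. How often this gives p<0.05.** Simulation with no BCG effect on any readout: 402 per arm, gamma-Poisson events with k = 0.36, 80% of events sampled, within-person correlation 0.3 (assumed), arm difference weighted as in a random-intercept model with a cluster-robust test, 2,000 runs per row. Every row has overall rate ratio 0.80.

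| Viral share, control | Viral / non-viral rate ratio | Viral share, BCG | d (SD) | Mean arm difference (SD) | p<0.05 |
|---|---|---|---|---|---|
| 50% | 0.80 / 0.80 | 50% | 1.0 | −0.001 | 5.7% |
| 50% | 0.60 / 1.00 | 37.5% | 0 | −0.002 | 5.1% |
| 50% | 0.60 / 1.00 | 37.5% | 0.25 | −0.033 | 7.5% |
| 50% | 0.60 / 1.00 | 37.5% | 0.5 | −0.064 | 15.1% |
| 50% | 0.60 / 1.00 | 37.5% | 1.0 | −0.124 | 39.9% |
| 50% | 0.60 / 1.00 | 37.5% | 1.5 | −0.185 | 63.2% |
| 30% | 0.33 / 1.00 | 12.5% | 0.5 | −0.089 | 23.5% |
| 30% | 0.33 / 1.00 | 12.5% | 1.0 | −0.174 | 67.1% |

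The simulated differences match −0.125d, and −0.175d for the 30% share. The first two rows show what the bias needs: selective prevention and a readout that varies by event type. Without either, the error rate stays near 5%.

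**The case against.** The strongest reply is that section 17.6 may not intend a Tier 3 treatment test. It speaks of longitudinal trajectories and of summaries by time point, and Tier 3 has events rather than time points. This ambiguity is real. But the sentence covers all tiers and nothing takes Tier 3 out, so a laboratory analyst following it would fit the model there. If Tier 3 was not meant, one clause settles it.

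Second, the objectives in section 2.2.2 and the analyses in 17.6 are labelled exploratory, and the exacerbation-pathogen objective is to relate one response to another, not to contrast the arms. That limits the weight of the point. It does not make a p-value from this comparison a valid test of a BCG effect on immune response.

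Third, the spurious shift is small in SD terms and the inputs are assumed. This stands: a rejection rate quoted without the shift would make the problem look larger than it is. The readouts to be modelled are also still to be chosen, so no SD difference between event types can be fixed in advance.

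A reader might infer that any Tier 3 arm difference is an artefact. The documents do not support that. Tier 3 includes anti-BCG antibodies, and Appendix A1.1 reports that anti-BCG responses rise after vaccination, so a difference there would largely be a direct vaccine response. For the other readouts, the two sources cannot be told apart; that does not mean the direct effect is absent.

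**Conclusion.** The point holds as a matter of interpretation in an exploratory tier. As written, section 17.6 allows treatment effects with p-values on Tier 3 readouts. For cytokines and pathogen antibodies such an effect cannot be divided into a BCG effect on the immune response and a change in which exacerbations occur, who has them and who returns samples. Anti-BCG antibodies are less affected.

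On the central assumptions (50% viral share, viral-only prevention, overall rate ratio 0.80, 80% of events sampled), the spurious shift is about 0.06 to 0.12 SD for event types that differ by 0.5 to 1 SD, with p<0.05 in about 15% to 40% of trials. It disappears if BCG prevents all types equally and the readout is unrelated to who exacerbates.

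A reader might also infer that the trial's main conclusions are at risk. They are not: the primary and secondary results do not rest on these models, and the scheduled Tier 1 and Tier 2 comparisons do not depend on having an exacerbation.

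**What to change.** In section 17.6:

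- Take treatment-effect estimates and p-values for immune response from the scheduled Tier 1 and Tier 2 samples only.
- Present Tier 3 readouts descriptively by arm and by the adjudicated aetiology already collected under section 8.2.2. State that they are conditional on a sampled exacerbation.
- Report the fraction of exacerbations with returned samples, by arm.
- Base any Tier 3 comparison between arms on event rates per person-year by pathogen finding, in the IGRA-negative analysis population that sections 9.9 and 14.2.1 define. Add the caveat that these rates still depend on sample return in an open-label trial.

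Descriptive summaries by treatment group are already planned and no new data are needed, so the change is to analysis wording. The cost is one less inferential claim from an exploratory tier.

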2.2.2 Mechanistic aims and objectives

Specific exploratory immunology objectives are to:

- Characterise cellular and molecular immune responses induced by vaccination (BCG-specific and non-specific) and to pathogens identified during any exacerbations.
- To relate responses induced by BCG to the level of protection BCG affords against exacerbations.
- To relate exacerbating pathogen-specific response (if it occurs) to immune response induced by the BCG vaccine, in order to identify biomarkers that predict BCG-associated protection from exacerbations.

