7.3 Overview of tissue sample collection

Blood samples will be collected from all participants of the trial at baseline. Some participants will be asked to provide additional blood samples at 1, 3 and 12 months. Participants will be asked to give consent to provide sputum samples, combined nasal and throat swabs at every AECOPD. Dried blood spot tests (DBS) will be completed at baseline, 3 months and 12 months follow up. Participants will also complete DBS test at every AECOPD if consented to do so.

Blood samples will be taken and processed at the local GP/NHS hospital sites. Samples will be frozen and stored at the GP/hospital site and then transported back to the Clinical Immunology Service at the University of Birmingham for longer term storage. Sample storage will be recorded in STABILISE lab file. Sputum, throat/nasal swabs and DBS tests will be sent directly to the Clinical Immunology Service at the University of Birmingham for receipt, processing and storage.

At the University of Birmingham, it is mandated that laboratories work to Good Clinical Practice.

Optional consent will be sought from participants to store any remaining blood samples after this trial for use in future research which conforms to all relevant legal, governance and ethical requirements. If consent for long term storage is not given, then these samples will be disposed of in accordance with the Human Tissue Authority's Code of Practice.

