8.2 Main trial outcomes

8.2.1 Primary outcome(s)

The primary outcome is moderate to severe AECOPD rate over 12 months follow up from IMP administration date (or from the date of randomisation if no treatment was administered). This is defined by the clinical adjudication committee and will be based on an assessment of:

- basic patient details
- healthcare utilisation (taking additional antibiotics and/or steroids, as recorded in the medical record, including prescription data),
- patient-reported symptoms of the AECOPD
- laboratory results from patient-provided sputum, saliva, nose/throat swabs and DBS samples following an exacerbation

Severe events are defined by additional hospitalisation. Confirmation of events as stated in section 8.1, will occur via the CAC. Terms of reference for the CAC will be set.

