17.4.1 Tier 1 outcomes (all cohort 800 participants)

All outcomes will be recorded at the pre-randomisation baseline visit and then at 1, 3 and 12 months post randomisation/vaccination (for the control/BCG vaccine groups respectively)

- Anti-BCG antibody responses, as obtained from ELISAs to detect IgG, IgA and IgM responses to whole BCG organism, proteinaceous (Ag85) and a non-proteinaceous (Lipoarabinomannan) antigen
- Cytokines: IL-1B, IL-6, TNFα and IL-10

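### Section 17.6 relates immune readouts taken up to month 12 to exacerbation rates without a time order, so a marker changed by past exacerbations can look like a correlate of protection (minor, exploratory analysis)

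*Protocol*

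**What the plan says.** Two sentences of Protocol Section 17.6 set the models. The first is "Associations between longitudinal samples and exacerbation rates will be explored through negative binomial mixed effects models". The second is "Associations between immune responses to BCG vaccination and exacerbations will be explored through negative binomial mixed effects models". In a negative binomial model the exacerbation count is the response, so the readouts enter as covariates. The section promises estimates of time and treatment effects with 95% confidence intervals (for the first model also two-sided p-values), and calls the mechanistic analyses largely exploratory. It names no landmark, lag or adjustment for earlier exacerbations, and sets no separate role for the month-12 sample.

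On sampling, Section 17.4.1 says of Tier 1: "All outcomes will be recorded at the pre-randomisation baseline visit and then at 1, 3 and 12 months post randomisation/vaccination". Section 17.4.2 gives Tier 2 the same times. Section 7.3 differs for the whole cohort: "Dried blood spot tests (DBS) will be completed at baseline, 3 months and 12 months follow up". The schedule in Section 9.8 also shows no month-1 dried blood spot.

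On the rate, Section 8.2.1 defines only one: "moderate to severe AECOPD rate over 12 months follow up from IMP administration date", or from randomisation where no vaccine was given. Sections 9.5 to 9.7 ask at month 3 about exacerbations since baseline, and at month 12 about the previous 9 months. Section 9.8 ends at month 12.

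On purpose, the second bullet of Section 2.2.2 is to relate BCG-induced responses to the level of protection against exacerbations.

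**The concern.** A correlate of protection has to be measured before the events it is said to protect against. By month 12 every counted exacerbation has already happened. By month 3 about a quarter have. An exacerbation, or the steroids and antibiotics given for it, may itself move a cytokine level or a leukocyte phenotype. If it does, a model with the exacerbation rate as response and the readout as covariate finds an association that runs from event to marker.

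A larger sample does not cure this: the bias stays and the standard error shrinks, so the risk is greatest in Tier 1, which is the whole cohort. At stake is the interpretation of the exploratory mechanistic results, where a consequence of exacerbation could be read as a marker of vaccine protection.

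**Working it through.** **Inputs from the protocol.** Control rate 2.25 and BCG rate 1.8 per person-year, dispersion k = 0.36, 90% power, 5% type 1 error and 10% loss (Section 14.1); two-sided tests (Section 14.2); Tier 2 of 80 participants (Section 17.5). Section 17.6 gives no figure for the analysis in question.

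**Check that these inputs are the plan's own.** With n per group = (z_a·√V0 + z_b·√V1)² / (ln RR)²:

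- V1 = 1/2.25 + 1/1.8 + 2(0.36) = 1.72
- V0 at the pooled rate 2.025 = 2(1/2.025 + 0.36) = 1.708
- n = (1.960·1.307 + 1.282·1.311)² / (ln 0.8)² = 361.4

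This reproduces the stated 361 to rounding. Then 361/0.9 = 401.1, so 402 per group and 804 in total. With 10% loss, 804·0.9 = 724, so about 720 are analysed.

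**Events already past when the sample is taken**, at a constant rate. The chance of at least one earlier event in a control participant is 1 − (1 + k·r·t)^(−1/k).

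| Sample | Share of 12-month events already past | Controls with at least one earlier event |
|---|---|---|
| Month 1 | 1/12 = 8% | 17% |
| Month 3 | 3/12 = 25% | 40% |
| Month 12 | 100% | 81% |

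**Simulation of a null marker.** Counts are gamma-Poisson with the rates and k above. The marker has no effect on exacerbations. Each event in the 3 months before a sample shifts that readout by b SD. Both b and the 3-month duration are assumptions. The models are negative binomial regressions, adjusted for arm and with no random effects, at 300 to 400 trials per setting. Ranges cover repeated runs. Entries are the percentage significant at the two-sided 5% level.

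| Model | b = 0.1 | b = 0.2 | b = 0.3 |
|---|---|---|---|
| Month-12 readout against 12-month rate, n=720 | 24–26% | 66–72% | 95–97% |
| Same, n=80 | 6–12% | 10–19% | 24–25% |
| Each readout against the count reported at the same visit, n=720 | 57% | 99% | 100% |

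At n=720 the rate ratio per SD is about 1.04, 1.09 and 1.13 in the first row, and 1.07, 1.15 and 1.23 in the third. With b = 0 the rejection rate is 3 to 7%, so the excess comes from the time order.

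**Sensitivity to how long the shift lasts**, b = 0.2, month-12 readout against the 12-month rate:

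| Duration | n=720 | n=80 |
|---|---|---|
| 2 weeks | about 6% | about 5% |
| 1 month | 10–18% | 7–10% |
| 3 months | about 70% | 10–19% |
| Permanent | 100% | 84–89% |

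**The remedy under the same conditions.** The month-3 readout against the months 3 to 12 count, with offset ln 0.75 and adjusted for earlier exacerbations, gives a rate ratio of 1.00 and about 3 to 10% significant across settings. The adjustment is needed: under a permanent 0.2 SD shift, the month-3 landmark without it still rejects in 14 to 20% of trials at n=722.

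**The case against.** The strongest reply has four parts.

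*Time order in an exploratory model is analysis-plan detail, and the window is not written in Section 17.6.* The second half is true: the 12-month window is inferred from the only rate defined. But the response, the covariates and the sampling times are fixed in the protocol, and for the month-12 sample no window after it exists. Exploratory status guards against over-reading chance findings; this bias is systematic.

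*Mixed models reporting time effects imply repeated interval counts rather than one 12-month total.* That is a fair reading. It does not remove the problem, because the visit questionnaires look backward. Pairing a count with the sample from the same visit puts every event before its readout, and the simulated bias is then larger.

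*The size is assumed.* This stands. The protocol gives no effect of an exacerbation on any readout, nor its duration, and the result runs from nominal to 100%. None of the simulations used random effects. The shift is more plausible for cytokines and cell phenotypes than for anti-BCG antibody, the first Tier 1 readout listed.

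*The protocol does not promise prediction from this model.* A reader might infer otherwise from "in order to identify biomarkers that predict BCG-associated protection from exacerbations". Those words close the third bullet of Section 2.2.2, which concerns pathogen-specific responses. The matching aim, in the second bullet, is associational. A reader might also infer that a fair share of positive findings will be consequences of exacerbation. Nothing in the protocol allows that share to be computed.

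**Conclusion.** The point holds as a minor one about exploratory analysis. As written, Section 17.6 allows a month-12 readout, or a readout paired with its same-visit count, to stand as a correlate of protection when it may only record exacerbations already past. That month-12 readouts can relate only to earlier events follows from the protocol's own schedule. How much this matters depends on an undocumented shift: about 25 to 97% false positives at n=720 and 6 to 25% at n=80 for 0.1 to 0.3 SD lasting 3 months, close to nominal if it fades within 2 weeks, and none if there is no shift. Baseline readouts and the randomised comparison are not affected.

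**What to change.** In Section 17.6, state that a readout used as a predictor or correlate of protection is related only to exacerbations after that sample. The usable samples are baseline, month 1 in Tier 2, and month 3. Include an offset for the remaining time and adjust for exacerbations before the sample and in the prior year. A landmark model or an equivalent lagged-interval model would serve. Analyse month-12 readouts as outcomes, and describe any association between them and earlier exacerbations as non-predictive.

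Reconcile Sections 17.4.1 and A1.1 with Sections 7.3 and 9.8 on whether the whole cohort gives a month-1 dried blood spot, since this decides which early Tier 1 samples can be used.

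The cost is wording. No new data are needed: exacerbation forms are completed at each event (Section 11.2), and prior-year exacerbations are collected at baseline (Section 6.2). The downside is that the 3-month model uses about 75% of events (9 of 12 months).
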